6.10.2. Other Secondary Efficacy Analyses

6.10.2.1. Tumor assessment including tumor size evaluation

For the FAS population, the waterfall plot of the best percentage change in tumor size will be provided. Also, line plot of percent change from baseline in tumor size may also be provided. Percent change from baseline in tumor size is calculated as follows and the smaller means better:

- Percent change from baseline = $(SUM_{Postbaseline} - SUM_{Baseline}) \times 100 / SUM_{Baseline}$,
- SUM = Longest diameter for extranodal lesions + short axis diameter for nodal lesions ,

where SUM is calculated only when all target/measurable lesions observed at baseline are measured.

Listings will be prepared presenting relevant information on response (response on target lesions including the percentage changes, response on non-target lesions, new lesions and overall response for each tumor assessment) for the FAS population.

6.10.2.2. Other efficacy outcomes

The overall survival (OS), the progression-free survival (PFS) and the duration of response (DOR) will be evaluated using the Kaplan-Meier method as described bellow.

For the FAS population, a listing of efficacy outcomes (i.e. BOR, OS, PFS and DOR) will be provided.

6.10.2.2.1. Overall Survival

The OS is defined as the time from the date of the first infusion of the study drug to the date of death from any cause. If a patient is not known to have died on or before the date of data cut-off, the OS will be censored on the last date (on or before the cut-off date) the patient was known to be alive.

For the FAS population, the number of events and the OS will be summarized by part and cohort.

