Investigational Product, Dosage, and Mode of Administration or Intervention:**Part A**

- Cohort 1: 15 mg/kg of olaratumab on Day 1 and Day 8, and 25 mg/m² of doxorubicin on Day 1, Day 2, and Day 3 of every 21-day cycle.
- Cohort 2: 15 mg/kg of olaratumab on Day 1 and Day 8, and 75 mg/m² of doxorubicin on Day 1 of every 21-day cycle.
- Cohort 3: 20 mg/kg loading dose of olaratumab on Day 1 and Day 8 in Cycle 1, followed by 15 mg/kg on Day 1 and Day 8 in subsequent cycles, and 75 mg/m² of doxorubicin on Day 1 of every 21-day-cycle.

Part B

This part consists of 1 dose level: 15 mg/kg of olaratumab on Day 1 and Day 8 of every 21-day cycle.

Planned Duration of Treatment:

Patients will be on treatment until one of the discontinuation criteria is met.

Treatment period: 21 days/cycle

Follow-up Period: 28 days

Criteria for Evaluation:

Safety: Dose-limiting toxicities, treatment-emergent adverse events (TEAEs) using Common Terminology Criteria for Adverse Events (CTCAE) version 4.03 and the Medical Dictionary for Regulatory Activities (MedDRA), laboratory evaluations, vital signs, electrocardiograms and cardiac function as measured by echocardiogram.

Bioanalytical: Serum concentrations of olaratumab (Part A and B) and plasma concentrations of doxorubicin (Part A).

Pharmacokinetics: The primary parameters for analysis will be maximum observed concentration (C_{max}) and area under the concentration-time curve (AUC) from time 0 to the last time point with a measurable concentration, and AUC from time 0 to infinity of olaratumab and doxorubicin. Other noncompartmental parameters, such as half-life, clearance, and volume of distribution, may be reported.

Efficacy: Antitumor activity according to Response Evaluation Criteria in Solid Tumors version 1.1.

Biomarkers: Biomarkers related to the mechanism of olaratumab, the PDGF signaling pathway, and the pathobiology of cancer.

Statistical Methods:

Safety: Dose-limiting toxicities will be listed and summarized by frequency. Adverse events (AEs), including TEAEs, will be listed and summarized in frequency tables using MedDRA. Severity of AEs will be classified using CTCAE version 4.03. Other safety data, such as laboratory tests, echocardiography, and vital signs, will be listed and summarized, if appropriate.

Efficacy: Efficacy data will be listed. Also, efficacy data will be summarized using frequency table or summary statistics, depending on the characteristics of the data.

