- The patient has evidence of objective progressive disease by radiological assessments (RECIST version 1.1) or deteriorating clinical symptoms of progressive disease. (Patients with objective progressive disease can be treated continuously based on the clinical symptoms at the discretion of the investigator.)
- The patient experiences unacceptable toxicity.
- The patient is significant noncompliant with study procedures and/or treatment (Section 7.6).
- The patient becomes pregnant.
- Both doxorubicin and olaratumab in Part A or olaratumab in Part B are discontinued (Section 7.2.2.1).

The reason and date of discontinuation will be collected for all patients. The date of discontinuation (for any of the above reasons) from study treatment is to be reported on the case report form (CRF). Patients who discontinue will have follow-up procedures performed as shown in the Study Schedule ([Attachment 1](#)).

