8.1.2.1. Serious Adverse Events

Planned surgeries should not be reported as SAEs unless the underlying medical condition has worsened during the course of the study.

Preplanned hospitalizations or elective procedures for underlying preexisting conditions that are already recorded in the patient's medical history at the time of study enrollment should not be considered SAEs. Hospitalization or prolongation of hospitalization without a precipitating clinical AE (eg, for the administration of study therapy or other protocol-required procedure) should not be considered SAEs.

An SAE is any AE during this study that results in one of the following outcomes:

- death
- initial or prolonged inpatient hospitalization (except for study drug administration)
- a life-threatening experience (ie, immediate risk of dying)
- persistent or significant disability/incapacity
- congenital anomaly/birth defect
- considered significant by the investigator for any other reason.

Important medical events that may not result in death, be life-threatening, or require hospitalization may be considered SAEs when, based on appropriate medical judgment, they may jeopardize the patient and may require medical or surgical intervention to prevent one of the outcomes listed in this definition.

Serious adverse events due to disease progression, including death, should not be reported unless the investigator deems them to be possibly related to the study drug.

Study site personnel must alert Lilly or its designee of any SAE within 24 hours of investigator awareness of the event via a sponsor-approved method. If alerts are issued via telephone, they are to be immediately followed with official notification on study-specific SAE forms. This 24-hour notification requirement refers to the initial SAE information and all follow-up SAE information.

If an investigator becomes aware of SAEs occurring after the patient's participation in the trial has ended, and the investigator believes that the SAE is related to a protocol procedure or study drug, the investigator should report the SAEs to the sponsor, and the SAEs will be entered in the Lilly Safety System.

Information on SAEs expected in the study population independent of drug exposure and that will be assessed by the sponsor in aggregate periodically during the course of the trial may be found in the IB.

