8.1.2.2.3. Follow-Up Visit

All AEs and SAEs, regardless of relatedness to study drug(s) or protocol procedures, occurring during the follow-up visit must be reported to Lilly or its designee. The follow-up visit starts on the day after the patient and the investigator agree to discontinue the study treatment and extends 28 days (± 5 days) from the last dose of study drug (olaratumab or doxorubicin). For patients who discontinue from the study treatment after a treatment delay, the follow-up visit can be performed after the allowed time window if it is difficult to perform the follow-up procedures within this time period. In such a situation, the follow-up visit should be performed as early as possible. At the end of the follow-up visit, the patient will be required to have specific safety assessments ([Attachment 1](#)).

Following the safety assessments, which mark the end of the follow-up visit, the patient will be discontinued from the study, unless there is an ongoing AE or SAE that is possibly related to study drug. In this instance, the patient should be monitored in subsequent follow-up visits until the event is resolved, the event is no longer considered to be drug-related, the event becomes stable or returns to baseline, a new treatment is initiated for the patient, or the patient dies or is lost to follow-up.

If it is deemed to be in the best interest of the patient to start a new anticancer treatment prior to the scheduled end of the follow-up visit, the follow-up visit duration may be shortened. In this case, the follow-up assessments should be completed prior to the initiation of the new therapy.

After the follow-up visit, AEs are not required to be reported unless the investigator feels the AEs were related to either study drug, drug delivery system, or a protocol procedure. If an investigator becomes aware of SAEs believed to be related to protocol procedures or study drug, the investigator should report the SAE to the sponsor, and the SAE will be entered in the Lilly Safety System.

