6.11.4. Deaths, Serious Adverse Events, and Other Significant Adverse Events

All deaths that occur after the first infusion of the study drug together with primary cause of death will be listed based on the FAS population.

The following items for AEs leading to death will be provided:

- Summary of AEs leading to death by PT
- Summary of AEs leading to death related to study drug by PT
- Listing of AEs leading to death

For the FAS population, the following items for treatment emergent SAEs will be generated:

- Summary of SAEs by PT
- Summary of SAEs related to study drug by PT

- Listing of SAEs

As other significant AEs, the following items will be provided:

- Summary of AEs leading to olaratumab discontinuation by PT
- Summary of AEs leading to doxorubicin discontinuation by PT in Part A
- Summary of AEs leading to olaratumab delay/omission/reduction/interruption by PT
- Summary of AEs leading to doxorubicin delay/omission/reduction/interruption by PT in Part A

The above four items will be repeated for AEs related to study drug. Also, a listing of AEs leading to study drug discontinuation (olaratumab or doxorubicin in Part A and olaratumab in Part B) will be prepared.

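### Minor: the SAP plans Kaplan-Meier overall survival, but the current protocol schedules no survival contact after the visit 28 days after last dose

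*SAP*

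**What the plan says.** **Analysis (SAP).** Section 6.10.2.2 states: "The overall survival (OS), the progression-free survival (PFS) and the duration of response (DOR) will be evaluated using the Kaplan-Meier method". It adds that "a listing of efficacy outcomes (i.e. BOR, OS, PFS and DOR) will be provided". Section 6.10.2.2.1 measures OS from first infusion to death from any cause, summarizes events and OS by part and cohort, and censors so that "the OS will be censored on the last date (on or before the cut-off date) the patient was known to be alive". Section 6.11.4 promises: "All deaths that occur after the first infusion of the study drug together with primary cause of death will be listed".

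**Data collection (protocol).** The synopsis gives "Follow-up Period: 28 days". Section 6.3.1 says: "Patients who discontinue will have follow-up procedures performed as shown in the Study Schedule". The schedules in Attachment 1 end at the Follow-Up column for both parts and have no survival row. Section 8.1.2.2.3 places the visit 28 days (±5) after last dose, after which "the patient will be discontinued from the study, unless there is an ongoing AE or SAE that is possibly related to study drug". Section 8.1.2.1 adds: "Serious adverse events due to disease progression, including death, should not be reported unless the investigator deems them to be possibly related" to study drug. Once a patient is off study, Table JGDK.8.1 asks only for possibly related SAEs that come to the investigator's attention, and marks them for the safety system but not the collection database. Protocol 10.6 names response rate, disease control rate (DCR), progression-free survival and duration of response, but not OS.

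**Stable disease (SD).** SAP 6.10.1 counts SD only if its criteria are met at least 6 weeks after first infusion. Attachment 1 allows the first on-study scan up to 14 days before Cycle 3 Day 1.

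**The concern.** Censoring at the last date known alive is sound when survival status is pursued to the cut-off. Here nothing scheduled pursues it. For most patients the rule becomes censoring about four weeks after last dose. Progression is one of the listed reasons for stopping, so censoring is tied to prognosis and is likely to be informative. Patients kept longer because of an ongoing, possibly related event are a selected group, so their later contact does not repair the gap. The listing of all deaths in SAP 6.11.4 has the same weakness after study exit.

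The stake is modest: a prespecified OS curve from about 6 patients per cohort that could be read as survival experience although it mostly describes time on treatment plus one month.

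A separate and smaller matter is that a compliant first scan can fall before the 6-week SD minimum. For short-lived stability, inclusion in DCR then depends partly on the day the scan was booked.

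**Working it through.** **1. No plan figure to reproduce.** The documents give no event count, precision or power for OS or DCR. Planned enrolment does check: 3 × 6 + 6 = 24.

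**2. Routes by which a death could reach the OS dataset.**
- Up to the follow-up visit: scheduled contact exists.
- After it, with an ongoing possibly related AE or SAE: further visits until that event is settled, for a subset only.
- After it, otherwise: no scheduled contact. Progression deaths are not reported as SAEs unless thought possibly related.
- Unscheduled knowledge: possible. The case report form is not among the documents.

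**3. Direction and size of bias.** The documents give no hazards, so all inputs here are assumptions: exponential times; post-treatment death hazard h2 = ln 2 / 8 = 0.0866 per month (median 8 months); on-treatment hazard h1 = h2 / r; median time to leaving treatment m = 2, 4 or 8 months, rate λ = ln 2 / m; censoring d = 28 / 30.44 = 0.92 months after leaving treatment.

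Worked case, r = 5, m = 2: h1 = 0.0173, λ = 0.3466, c = λ + h1 − h2 = 0.2773.
- True S(12) = e^(−(λ+h1)·12) + (λ/c)·[e^(−h2·12) − e^(−(λ+h1)·12)] = 0.0127 + 1.25 × (0.3536 − 0.0127) = 0.44.
- Beyond month 0.92, the ratio of recently stopped to on-treatment patients under observation is (λ/c)(e^(cd) − 1) = 1.25 × 0.2906 = 0.363. The hazard the curve sees is (0.0173 + 0.363 × 0.0866) / 1.363 = 0.036 per month, less in the first month. This gives a Kaplan-Meier value of about 0.66.
- Difference: 0.22.

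Simulation with 400,000 patients per setting gives the excess of the 12-month Kaplan-Meier value over the true value, in percentage points:

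| r | m = 2 | m = 4 | m = 8 |
|---|---|---|---|
| 1 | 0 | 0 | 0 |
| 2 | 12 | 11 | 8 |
| 3 | 17 | 16 | 11 |
| 5 | 22 | 20 | 15 |

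At r = 1 both values equal 2^(−12/8) = 0.354. The share of deaths within 12 months that fall after study exit is 27% to 60% at r = 1 and 57% to 79% at r = 5. The range moves with assumed post-treatment survival: at r = 5 the excess is about 17 to 23 points for a 4-month median and 10 to 15 for 16 months.

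**4. Scan window against the SD minimum.** Cycle 3 Day 1 is 2 × 21 = 42 days after first infusion, so the first scan may fall on days 28 to 42, and 14 of those 15 days precede day 42. If Cycle 3 Day 1 slips by 3 days the window is 31 to 45 (11 early days); by 6 days, 34 to 48 (8 early days). These are calendar days, not shares of patients. The next scheduled window is days 70 to 84.

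If every patient were scanned on days 35 and 77, with exponential progression of median 2 to 6 months (S(t) = 2^(−t/(30.44 × median))), then S(42) − S(77) = 0.204 to 0.106. That is 1.2 to 0.6 of 6 patients still stable on day 42 but left out of DCR. One patient moves DCR by 1/6 = 16.7 points, for example 4/6 = 66.7% (Wilson 95% CI 30.0 to 90.3) to 3/6 = 50.0% (18.8 to 81.2).

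**The case against.** **OS is descriptive and permitted.** It is not a study objective, and protocol 10.1 allows added exploratory analyses, so its absence from protocol 10.6 is not a contradiction. This stands and is the main reason for a minor rating.

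**The censoring rule is not itself faulty.** It is a normal rule; the gap is in finding deaths after exit. This stands, and it is why the per-patient dates should be kept.

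**Some deaths may be captured anyway.** The clause on progression deaths governs SAE reporting only, and SAP 6.11.4 expects deaths to be listed. A reader might infer that no death after exit can be known. The documents do not support that; they show only that no procedure looks for such deaths.

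**The versions differ.** SAP section 3 ties the SAP to the protocol approved on 9 December 2014, which is not supplied. The amendment (b) summary shows no change to survival follow-up, and the stated rationale for amendment (a) is only the addition of Cohort 3. The comparison is therefore with the current protocol, and nothing available suggests the older one differed on this point.

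**The 12-month figure is not a planned estimate.** Correct: the SAP names no landmark. The figure only illustrates how far the curve could be displaced.

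**The SD rule is deliberate.** A minimum duration is meant to exclude stability seen only earlier, and the response listing by assessment in SAP 6.10.2.1 already lets a reader find early-only SD. Both stand, so that part is optional.

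**Conclusion.** The mismatch holds, at minor severity. Under the current protocol, survival after the follow-up visit is not systematically collected, so a Kaplan-Meier OS curve would rest on censoring that is likely to be informative.

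A reader might infer that the curve is certainly too high by some 20 points. That does not follow. The direction depends on the death hazard being higher after treatment than on it, and there is no bias if the hazards are equal. The 0 to 22 point range rests on exponential times, an 8-month post-treatment median, treatment medians of 2 to 8 months and hazard ratios of 1 to 5, none of which is in the documents.

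A reader might also infer that the scan window makes DCR wrong. It does not. Patients still stable at a later scan and confirmed responders are unaffected, and the number affected depends on when sites actually scan, which the documents do not say.

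DLT and PK conclusions are unaffected.

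**What to change.** SAP wording only.

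- **6.10.2.2:** remove OS from the Kaplan-Meier sentence. In the efficacy listing, keep each patient's death date or last-known-alive date.
- **6.10.2.2.1:** delete the Kaplan-Meier OS summary.
- **6.11.4:** add: *Deaths from first infusion through 33 days after the last dose of study drug (28 days plus the 5-day visit allowance), and deaths known to have occurred later, will be counted separately by part and cohort; survival after the follow-up visit was not systematically collected.*

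A fixed day count is needed for two reasons. Protocol 8.1.2.2.2 ends the on-therapy period at the last dose, so an on-treatment class of deaths would be almost empty. A patient who dies before the follow-up visit also has no visit to close an interval defined by it.

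**Optional, 6.10.1:** keep the 6-week rule for the main DCR. Report the number of patients whose only SD was at a within-window pre-Cycle 3 scan before day 42, with a DCR that includes them as a sensitivity figure. It is an upper figure because it also admits patients who progress between the early scan and day 42: S(35) − S(42) = 5% to 2% under the assumptions above.

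The cost is one descriptive curve lost and a few counts added. No visits or scans change.

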6.10.2.2.2. Progression-free Survival

The PFS is defined as the time from the date of the first infusion of the study drug to the date of objectively determined PD or death from any cause, whichever is first. Censoring rules are described in [Table JGDK.6.1](#).

Table JGDK.6.1. Censoring rules

Situation	Date of Progression or Censoring	Outcome
-----------	----------------------------------	---------

Situation	Date of Progression or Censoring	Outcome
No baseline tumor assessments	Date of the first infusion of the study drug	Censored
Progression documented between scheduled visits	Earliest of the following dates: 
 • Date of radiological assessment showing new lesion (if progression is based on new lesion) • Date of last radiological assessment of measured lesions (if progression is based on increase in sum of measured lesions) 	Progressed
No progression	Date of last radiological assessment of measured lesions	Censored
discontinuation for undocumented progression	Date of last radiological assessment of measured lesions	Censored
Treatment discontinuation for toxicity or other reason	Date of last radiological assessment of measured lesions	Censored
New anticancer treatment started	Date of last radiological assessment of measured lesions	Censored
Death before first PD assessment	Date of death	Progressed
Death between adequate assessment visits	Date of death	Progressed
Death or progression after more than one missed visit	Date of last radiological assessment of measured lesions	Censored

For the FAS population, the number of events and the PFS will be summarized by part and cohort.

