Attachment 1. Protocol I5B-JE-JGDK Study Schedule

Study Schedule for Protocol I5B-JE-JGDK – Part A: Screening and Cycle 1

Relative day within a cycle	Screening			Cycle 1				Comments
	≤21	≤14	≤7	1	2	3	8	
Informed consent	X							Informed consent form signed (prior to performance of any protocol-specific tests/procedures and patients must be ≥ 20 years of age).
Medical history		X						Includes past and current medical conditions, treatments, and alcohol/tobacco use.
Pregnancy test			X					Serum or urine: Pregnancy test is only required for females of child-bearing potential.
Physical examination		X		X ^a			X ^a	Includes medical interview, height (at screening only), weight, and body surface area.
Vital signs		X		X ^b			X ^c	Pulse rate, respiration rate, temperature, and supine blood pressure will be measured.
ECOG performance status		X		X ^a				
NYHA classification		X						
ECG	X			See Attachment 4				Screening ECGs will be performed locally. Obtain ECGs before any associated blood draws.
Echocardiogram	X							Echocardiogram will be performed locally. Data obtained before patient's consent may be used as the screening data if the relevant tests are conducted within the allowed time window.
Hematology		X		X ^a			X ^a	
Serum chemistry		X		X ^a			X ^a	
Coagulation		X		X ^a				
Urinalysis		X		X ^a				
Hepatitis B and C virus	X							Includes tests for Hepatitis B surface antigen, Hepatitis B surface antibody, Hepatitis B core antibody and Hepatitis C antibody. Test for Hepatitis B DNA will be performed as necessary.
CTCAE v4.03 grading	X			X	X ^d	X ^d	X	Throughout study as needed.
Concomitant medications	X			X	X ^d	X ^d	X	
Radiological tumor assessment	X							Data obtained before patient's consent can be used as screening data if the relevant tests are conducted within the allowed time window.
PK sampling				See Attachment 4				
Immunogenicity sampling				See Attachment 4				
Blood sampling for translational research				X ^a				Plasma samples will be collected from whole blood.
Tumor tissue submission				X				If available.
Olaratumab administration				X ^e			X ^e	
Doxorubicin administration				X	X ^d	X ^d		

Study Schedule for Protocol I5B-JE-JGDK – Part A: Screening and Cycle 1

Abbreviations: CTCAE = Common Terminology Criteria for Adverse Events; DNA = deoxyribonucleic acid; ECG = electrocardiogram; ECOG = Eastern Cooperative Oncology Group; NYHA = New York Heart Association; PK = pharmacokinetic.

- a Predose only.

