- b Vital sign measurements will be obtained prior to and at the completion of each olaratumab administration, and prior to each doxorubicin administration.
- c Vital sign measurements will be obtained prior to and at the completion of olaratumab administration, and approximately one hour following the completion of olaratumab administration.
- d Cohort 1 only.
- e 15 mg/kg in Cohort 1 and 2, and 20 mg/kg as loading dose in Cohort 3.

Study Schedule for Protocol I5B-JE-JGDK – Part A: Cycle 2 and beyond

Relative day within a cycle	Cycle 2-6				Cycle 7-n		Follow-Up ^c	Comments
	1a	2	3	8	1b	8		
Allowance (days)	+3			±3d	+3	±3	±5	
Informed consent	X							Informed consent form signed (prior to beginning of Cycle 2).
Pregnancy test	X ^e				X ^e		X	Should be performed approximately every 6 weeks (i.e., at the beginning of Cycle 3 and every other cycle thereafter) during the study.
Physical examination	X ^e				X ^e		X	Includes medical interview, weight, and body surface area.
Vital signs	X ^f			X ^f	X ^f	X ^f	X	Pulse rate, respiration rate, temperature, and supine blood pressure will be measured.
ECOG performance status	X ^e				X ^e		X	
ECG	See Attachment 4							Obtain ECGs before any associated blood draws.
Echocardiogram	X ^e				X ^e		X	Should be performed locally at Cycles 5 and 7 (within 3 days prior to the treatment on Day 1, but re-measurement is not necessary in case of dose delay of Day 1) and follow-up visit.
Hematology	X ^e			X ^e	X ^e	X ^e	X	
Serum chemistry	X ^e			X ^e	X ^e	X ^e	X	
Coagulation	X ^e				X ^{e,h}		X	
Urinalysis	X ^e				X ^{e,h}		X	Should be performed approximately every 6 weeks (ie, at the beginning of Cycle 3 and every other cycle thereafter).
CTCAE v4.03 grading	X	X ^g	X ^g	X	X	X	X	Throughout study as needed.
Concomitant medications	X	X ^g	X ^g	X	X	X	X	
Radiological tumor assessment	X				X		X	Prior to Cycles 3 and 5 (no more than 14 days prior to Day 1 Cycle 3 and 5), then every 2-4 cycles as clinically indicated.
PK sampling	See Attachment 4							
Immunogenicity plasma sampling	See Attachment 4							
Olaratumab administration	X			X	X	X		
Doxorubicin administration	X	X ^g	X ^g					

Study Schedule for Protocol I5B-JE-JGDK – Part A: Cycle 2 and beyond

Abbreviations: CTCAE = Common Terminology Criteria for Adverse Events; ECG = electrocardiogram; ECOG = Eastern Cooperative Oncology Group; PK = pharmacokinetic.

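### SAP Table JGDK.6.1 leaves three PFS entries wrong or undetermined: patients with no post-baseline scan, missed visits after Cycle 5, and the censoring date after a gap

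*SAP*

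**What the plan says.** SAP 6.10.2.2.2 fixes the time origin: "The PFS is defined as the time from the date of the first infusion of the study drug to the date of objectively determined PD". Death also counts as an event if it comes first. Table JGDK.6.1 then assigns dates by situation.

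- Four rows for patients without a PFS event (no progression, undocumented progression, stopping for toxicity or another reason, new anticancer treatment) censor at "Date of last radiological assessment of measured lesions". Nothing limits this to scans after baseline.
- The only row that censors at first infusion is "No baseline tumor assessments".
- "Death before first PD assessment" is an event on the date of death.
- "Death or progression after more than one missed visit" is censored, again at the last radiological assessment. Neither document defines a missed visit, or the adequate visit that another row mentions.

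In Protocol Attachment 1 the baseline scan belongs to the screening column of up to 21 days before dosing, and a scan made before "consent can be used as screening data if the relevant tests are conducted within the allowed time window". On-study scans are fixed before Cycles 3 and 5, "then every 2-4 cycles as clinically indicated", with a further scan at the follow-up visit. Part B has the same scan schedule.

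**The concern.** A censoring table should give every patient exactly one date and one status, fixed before outcomes are known. This one falls short in three places.

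1. A treated patient who leaves alive before any on-study scan has a baseline scan, so the no-baseline row does not apply. The other rows point to the screening scan, which precedes the time origin. This is foreseeable: the FAS takes in anyone given any amount of study drug, and the first on-study scan is due only before Cycle 3.
2. Counting missed visits requires knowing when visits were due. After Cycle 5 the protocol gives a range of intervals, so the same data can yield an event or a censored time.
3. The row for progression between scheduled visits uses the last-assessment wording for the progression scan itself when the lesion sum has grown. The missed-visit row uses the same wording for its censoring date. Read consistently, a patient whose progression is found after a gap would be censored on the progression scan and credited with the whole gap.

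At stake is whether individual PFS entries are valid and reproducible in an open-label study with cohorts of about 6.

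**Working it through.** The plan states no figure to reproduce here; the check is date arithmetic.

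**Baseline scan only, patient alive.** PFS = censoring date − first-infusion date. A screening scan taken 21 days before dosing gives −21 days; one taken the day before gives −1. If a day is added to durations, the range is −20 to 0.

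Effect on the curve, for an assumed cohort of 6: events at Days 43, 85, 127 and 211, one patient censored at Day 169, and the sixth censored at either Day −14 or Day 0. In both versions five patients are at risk at Day 43, and the estimate runs 4/5 = 0.8, × 3/4 = 0.6, × 2/3 = 0.4, × 0/1 = 0. The curves are identical. What suffers is the listing and any minimum or range.

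**Baseline scan only, patient dies.** The row for death before the first PD assessment makes this an event at death. If the patient had by then missed both the Cycle 3 and Cycle 5 scans, two visits are missed, so the last row also applies and censors at the screening scan. The table gives no order of precedence.

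**Missed visits after Cycle 5.** With 21-day cycles, Cycle 5 Day 1 is 1 + 4 × 21 = Day 85. Take that as the last scan, let progression be seen g cycles later, and let scans be due every k cycles. The missed scans are the multiples of k strictly below g. More than one is missed once g exceeds 2k: 12 weeks for k = 2, 18 for k = 3, 24 for k = 4.

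| Gap (weeks) | Progression day | Missed, k = 2 | Missed, k = 3 | Missed, k = 4 | Status |
|---|---|---|---|---|---|
| 12 | 169 | 1 | 1 | 0 | event on all |
| 15 | 190 | 2 | 1 | 1 | depends on k |
| 18 | 211 | 2 | 1 | 1 | depends on k |
| 21 | 232 | 3 | 2 | 1 | depends on k |
| 24 | 253 | 3 | 2 | 1 | depends on k |
| 27 | 274 | 4 | 2 | 2 | censored on all |

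At 18 weeks the 2-cycle grid misses the Cycle 7 and Cycle 9 scans and censors at Day 85. The 3-cycle grid misses only Cycle 8, the 4-cycle grid only Cycle 9, and both give an event at Day 211.

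Effect on the curve, for a second assumed cohort of 6: events at Days 43, 85 and 127, censored times at Days 127 and 169, and the sixth patient as above. With an event at Day 211 the estimate at Day 127 is 5/6 × 4/5 × 3/4 = 0.50, and it falls to 0 at Day 211. With censoring at Day 85 it is 5/6 × 4/5 × 2/3 = 0.444 at Day 127, and the Day 211 event disappears.

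**Which last scan.** In the same example, if the missed-visit row applies, the scan before the gap gives censoring at Day 85. The most recent scan gives censoring at Day 211, a difference of 126 days. For a death after a gap this problem does not arise, because no scan sits at the end of the gap.

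**The case against.** The strongest reply is that these are drafting gaps with little reach, and much of it stands.

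- A reader might infer that there is no scan schedule after Cycle 5. There is one: 2 to 4 cycles, plus a follow-up scan. It lacks a fixed interval, and the ambiguity is bounded at both ends.
- A reader might infer that progressions in compliant patients can be discarded. Counted in cycles, they cannot. A patient scanned before Cycle 5 and next before Cycle 9 has missed at most one visit even on the 2-cycle grid, and the rule needs more than one.
- A reader might add the dosing delays in Attachment 5 to stretch a compliant interval. Those scenarios cover Cycles 2 to 5 only, and only the doxorubicin delays move the next Day 1. Scans scheduled by cycle move with the cycles.
- A reader might infer that the negative times bias the curve. They do not, as shown above.
- The follow-up scan reduces the number of baseline-only patients. It does not remove them: Protocol 8.3 lets repeat radiology be omitted after discontinuation when clinical progression is clear.
- A rule meant to set late progression aside would sensibly censor before the gap. That is the likely intent, but the wording does not say so, and the same words mean the progression scan elsewhere in the table.
- PFS is an additional descriptive outcome. ORR and DCR are the main efficacy measures, tolerability rests on DLTs, and tumour assessments and PFS are listed by patient, so a reclassification would be visible.

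**Conclusion.** The point holds as a minor one. Applied literally, the table gives a living baseline-only patient a PFS of −21 to −1 days when the scan preceded the infusion day. It gives two conflicting outcomes for a baseline-only patient who dies after missing both fixed scans. It cannot classify progression or death seen more than 12 and up to 24 weeks after the Cycle 5 scan, and it can place a censoring date on the progression scan itself.

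The first defect affects the listing and ranges only. The missed-visit defects can turn an event into a censored time or move a censoring date, for a patient who is one of about 6 in the cohort. The 12- and 24-week limits assume nominal 21-day cycles and a last scan before Cycle 5; the Kaplan-Meier figures rest on invented data and only illustrate direction. That compliant patients are unaffected assumes visits are counted in cycles, which the SAP does not state. No primary conclusion or study decision is threatened.

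**What to change.** Amend Table JGDK.6.1 as follows.

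1. Add a row: no post-baseline assessment and no death, censored at first infusion.
2. State which row takes precedence when a baseline-only patient dies after missing both the Cycle 3 and Cycle 5 scans.
3. Define a missed visit against the existing schedule: the Cycle 3 and Cycle 5 scans, then the longest permitted interval of 4 cycles. Count in cycles, so that dose delays do not create missed visits. Define an adequate assessment in the same footnote.
4. In the missed-visit row, set the censoring date to the last adequate assessment before the gap, or to first infusion if there is none after baseline.

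A single limit in calendar weeks would be a poorer choice: it could overturn cases that the fixed Cycle 3 and Cycle 5 scans now settle, and it would not move with cycle delays.

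The cost is a short table edit with no new data. The SAP still describes two Part A cohorts where the protocol has three, so it could be made in the same revision. The downside is that some late progressions remain events under the 4-cycle interval; in the example, Day 211 would count as an event.
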